### **16.1.9 Documentation of Statistical Methods**

[SimpliciTB SAP, Version 3.0, 26MAY2021](#)

[SimpliciTB SAP, Note to File 1 for SAP Version 3.0, 11NOV2021](#)

[SimpliciTB SAP, Note to File 2 for SAP Version 3.0, 11NOV2021](#)

[SimpliciTB SAP, Note to File 3 for SAP Version 3.0, 11NOV2021](#)

**Version History:**

Version Number/Date	Change
0.1 / 15June2018	1 st draft circulated
0.2 / 27June2018	2 nd draft AC discussed with CM
0.3 / 28June2018	3 rd draft circulated
0.4 / 29June2018	4 th draft circulated following comments from CM and MO
0.5 / 13August2018	5 th draft circulated following rework by CM
0.6 / 31Augut2018	6 th draft circulated to wider group
1.0 / 07November2018	Version 1.0 following external review
1.1 / 15March2019	Updated to include details of interim analysis;
1.2 / 11April2019	Updated following comments on v1.1
1.3 / 25April2019	Updated following comments on v1.2
1.4 / 10May2019	Updated following comments on v1.3
1.5 / 17May2019	Updated following comments on v1.4
2.1 / 25June2020	Adding COVID clause Adding minor clarification to the text
2.2 / 24 September 2020	Combining efficacy and safety SAP information
2.3 / 01 December 2020	Incorporation of comments after online review
2.4 / 10 December 2020	Incorporation of comments following review meeting
2.5 / 22 March 2020	New draft following internal review. Circulated to TBA.
2.6 / 21 May 2021	New draft following review with TBA.
3.0 / 26 May 2021	Version 3.0 following the combination of the efficacy and safety SAPs

## List of Abbreviations

AE	Adverse Event
ALP	Alkaline Phosphatase
ALT	Alanine Aminotransferase
ANC	Absolute Neutrophil Count
AREDS2	Age Related Eye Disease Scale 2
AST	Aspartate Aminotransferase
ATC	Anatomical Therapeutic Chemical
B	Bedaquiline
BLQ	Below the Limit of Quantitation
BMI	Body Mass Index
BPaMZ	Combination of Bedaquiline plus Pretomanid plus Moxifloxacin plus Pyrazinamide
CPK	Creatinine Phosphokinase
DMID	Division of Microbiology and Infectious Disease
DSMC	Data Safety Monitoring Committee
DR-TB	Drug-resistant tuberculosis
DS-TB	Drug-sensitive tuberculosis
ECG	Electrocardiogram
(e)CRF	(electronic) Case Report Form
GGT	Gamma-glutamyl Transferase
HeR	Heart Rate
HIV	Human Immunodeficiency Virus
HGB	Hemoglobin
HRZE	Isoniazid, Rifampicin, Pyrazinamide, Ethambutol
HR	Isoniazid plus Rifampicin combination tablet
ITT	Intent to Treat
IMP	Investigational Medication Product
IWRS	Interactive Web Response System
MeDRA	Medical Dictionary for Regulatory Activities
mITT	Modified Intent to Treat
MDR-TB	Multi Drug Resistant Tuberculosis
MGIT™	Mycobacterial Growth Indicator Tube
Pa	Pretomanid
PD	Pharmacodynamic
PP	Per Protocol
PK	Pharmacokinetic
PT	Preferred term
PR	PR interval – time from start of P wave to start of QRS complex on ECG
QT	QT interval – time from start of Q wave to end of T wave on ECG
QTc	QT interval corrected for heart rate
QTcB	QT interval corrected for heart rate using Bazett's formula
QTcF	QT interval corrected for heart rate using Fridericia's formula
QRS	QRS complex (ventricular depolarization) on ECG
RBC	Red Blood Cell
RR	RR interval – time between two QRS complexes on ECG
SAP	Statistical Analysis Plan
SOC	System Organ Class
TB	Tuberculosis
TB-mITT	TB Specific Modified Intent to Treat
TEAE	Treatment Emergent Adverse Event
ULN	Upper Limit of Normal
WBC	White Blood Cell
XDR-TB	Extensively Drug Resistant Tuberculosis

## 1. Introduction

This document outlines the statistical analysis for both efficacy and safety. This includes, but is not limited to, the efficacy primary endpoint, secondary efficacy and safety endpoints, populations, TB symptoms, EQ5D, adherence and weight. Summaries of plasma drug concentrations and PK parameters will also be described.

SimpliciTB is a multi-centre, open-label, randomised clinical trial in drug sensitive tuberculosis (DS-TB). DS-TB participants should be sensitive to rifampicin and isoniazid and either newly diagnosed for tuberculosis (TB) or have a history of being untreated for at least 3 years after cure from a previous episode of TB.

Participants who are drug resistant (DR-TB) will also be enrolled into the study and will receive the same experimental treatment, except that they will be treated for a longer period of time due to the high degree of pyrazinamide resistance expected in this group. These participants will not be randomised. DR-TB participants should be resistant to rifampicin or isoniazid.

SimpliciTB will evaluate and support that, in addition to previous studies evaluated with BPaMZ, the drug regimen (BPaMZ) will be safe, effective, and well-tolerated and could potentially shorten the current treatment duration compared to standard HRZE/HR treatment for participants with DS-TB disease. This trial will also evaluate if this drug regimen (BPaMZ) given for 6 months will be safe and effective in DR-TB disease. All participants will be followed for 2 years after enrolment.

For participants with DS-TB, the experimental arm (4BPaMZ) will be compared to the control arm (HRZE/HR) in all analyses (unless otherwise stated). There will be no formal comparisons for participants with DR-TB.

While SimpliciTB is an open label study, only members of the Data Safety Monitoring Committee (DSMC) and the unblinded statistician(s) will have access to data grouped by study arm. Access to data grouped by study arm by investigators, CRO and TB Alliance study team should not occur. In addition, site staff will be strongly discouraged from attempting to aggregate data by treatment arm at a site level. In order to protect the safety of study participants, TB Alliance staff who do not work directly with study conduct will require access to aggregated safety data as part of study safety oversight and for the purpose of making strategic study decisions. In addition, if there are identified potential safety concerns that warrants a more frequent look at aggregated data compared to the DSMC meeting frequency, the medical monitoring team will require access to aggregated safety data.

Note: The protocol refers to three analysis populations (ITT, mITT and PP). In this SAP these are referred to as mITT, TB-mITT and PP. There are also two additional analysis populations outlined in the SAP. This is described in [Table 1](#).

Table 1: Analysis populations according to protocol and SAP

Analysis Populations	
Protocol	Statistical Analysis Plan
All randomised*	Intent to treat (ITT)
Safety*	Safety
Intent to treat (ITT)	Modified intent to treat (mITT)
Modified intent to treat (mITT)	TB-specific mITT (TB-mITT)
Per protocol (PP)	Per Protocol (PP)

\*Not formally defined in the protocol

### 1.1. Trial Intervention

Participants with DS-TB who are randomised to the intervention arm will receive: bedaquiline (200 mg daily for 8 weeks then 100 mg daily for 9 weeks); and pretomanid (200 mg daily), moxifloxacin (400 mg daily) and pyrazinamide (1500 mg daily) for 17 weeks (4BPaMZ).

Participants with DS-TB who are randomised to the control arm will receive the standard dose of isoniazid, rifampicin, pyrazinamide and ethambutol (HRZE) for 8 weeks followed by 18 weeks of isoniazid and rifampicin. This regimen will be administered according to weight band (HRZE/HR).

Participants with DR-TB will be treated with bedaquiline (200 mg daily for 8 weeks then 100 mg daily for 18 weeks); and pretomanid (200 mg daily), moxifloxacin (400 mg daily) and pyrazinamide (1500 mg daily) for 26 weeks (6BPaMZ).

### 1.2. Randomisation, Stratification and Blinding

Eligible participants with DS-TB will be randomised in the ratio 1:1 using an interactive web response system and stratified according to:

- HIV status (positive vs. negative)
- Cavitation (yes vs. no)

Participants, trial Investigators and staff, including laboratory staff, will not be blinded to treatment allocation during the treatment phase of the trial. See blinding plan for more detail.

## 2. Outcome Measures

### 2.1. Primary Efficacy Endpoint

The primary efficacy endpoint will be time to culture negative status in liquid media, up to 8 weeks. This will be assessed for superiority. The hypothesis is that the 4-month treatment regimen will be superior to control for participants with DS-TB. A modified intent-to-treat (mITT) analysis will be performed (as defined in §6.1).

## **2.2. Key Secondary Efficacy Endpoint**

A key secondary efficacy endpoint will be the proportion of participants who have an unfavourable outcome at 12 months. This will be assessed for non-inferiority using the 12% margin. The difference in proportions of unfavourable status at 12 months post-randomisation (non-inferiority comparison) will be performed for participants with DS-TB for the mITT, TB-mITT and PP analysis populations (as defined in §6.1).

## **2.3. Secondary Safety and Tolerability Outcomes**

All safety summaries in this section will be presented for all participants in the Safety population, as defined in §5, unless otherwise stated.

Adverse event verbatim reported terms will be coded by system organ class (SOC) and preferred term (PT) using the latest version of MedDRA.

Adverse events are defined as either:

1. Treatment emergent adverse events (TEAEs) which are adverse events (AEs) which started or worsened on or after the first administration of IMP up to and including 14 days after the last study drug administration, or
2. Post-treatment AEs which are AEs that start or worsen more than 14 days after the last administration of IMP.

Secondary safety and tolerability outcomes are outlined below in §2.3.1-2.3.7. These data will be presented as descriptive analyses, and no inferential tests will be carried out.

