### **3.3. Adequate Treatment**

The definition of adequate treatment sets a limit for the amount of treatment missed. Participants not taking the adequate amount of treatment by this definition will be excluded from the PP analysis (see [§6.2.3](#)).

Participants allocated to a 4 month regimen, to meet the definition of adequate treatment they must have taken at least 96 doses (80%) of their allocated 119 day (17 weeks) treatment regimen within 175 days of starting therapy (i.e. 17 weeks plus an allowable 56 day halt (including a maximum of 35 consecutive days) as per the protocol).

Participants allocated to a 6 month regimen, to meet the definition of adequate treatment they must have taken at least 146 doses (80%) of their allocated 182 day (26 weeks) treatment regimen within 238 days of starting therapy (i.e. 26 weeks plus an allowable 56 day halt (including a maximum of 35 consecutive days) as per the protocol).

Participants in the control arm are additionally required to have taken at least 80% of their allocated intensive treatment.

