### **3.6. Trial Timings**

Study Day 1 is defined as the date on which a participant is administered the first dose of the study medication. Other study days are defined relative to the Study Day 1 with Day 2 being the day after Study Day 1 and Day -1 being the day prior to Study Day 1.

For all safety endpoints, baseline is defined as the last non-missing measurement prior to first dose of study treatment unless otherwise stated.

In all analyses, visit date rather than day or week number will be used to define the timing of events. For participants treated with the 6-month regimens (HRZE/HR for DS-TB participants and 6mBPaMZ for DR-TB participants) this will be taken as a total of 26 weeks, i.e. 182 dosing days. For DS-TB participants randomised to 4 months of BPaMZ a total of 17 weeks (119 dosing days) is taken. As per the protocol, assessments should be collected as follows:

- Within  $\pm 3$  days of scheduled visit from day 1 to week 8
- Within  $\pm 5$  days of scheduled visit from week 12 to week 26
- Within  $\pm 14$  days of scheduled visit during the follow-up phase at or after month 6 to month 24.

Unscheduled visits and visits outside of these windows will be slotted into windows as appropriate. Visits falling outside of the defined protocol visit windows will be put into separate visits so that all data, both collected at scheduled and unscheduled time points, are used.

The **treatment period** is defined as either 17 or 26 weeks from start of therapy depending on allocated treatment regimen.

The **follow-up period** is defined as the period after the end of treatment to the end of follow-up.

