### **8.2.9. Additional TEAE summary**

The number and percentage of participants with the following specific TEAEs will be presented: grade 2, 3, or 4 myalgia, and grade 3 or 4 cardiac rhythm disturbances, grade 3 or 4 lipase, pancreatitis, peripheral neuropathy.

All AEs will be presented in a listing, which will specify whether they are treatment emergent or not.

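### Adverse-event percentages are counted over nominally 19 weeks on 4BPaMZ and 28 weeks on HRZE/HR, with no common-window companion table and no table of post-treatment events

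*SAP*

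**What the plan says.** SAP section 2.3 divides adverse events into two classes. Treatment-emergent events (TEAEs) start or worsen "on or after the first administration of IMP up to and including 14 days after the last study drug administration". The second class is "Post-treatment AEs which are AEs that start or worsen more than 14 days after the last administration of IMP".

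The length of the first window follows the length of the regimen. Section 3.6 sets this for the experimental arm: "For DS-TB participants randomised to 4 months of BPaMZ a total of 17 weeks (119 dosing days) is taken". For the 6-month regimens, "this will be taken as a total of 26 weeks, i.e. 182 dosing days". Section 1.1 agrees for the control arm, which receives HRZE "for 8 weeks followed by 18 weeks of isoniazid and rifampicin".

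The outcomes in section 2.3.2 and the tables in section 8.2 are counts and percentages of participants with TEAEs: overall, by severity, drug-related, serious, leading to discontinuation, fatal and liver-related. The tables by standardised MedDRA query added in Note to File 2 are also restricted to TEAEs. Events outside the window appear only under section 8.2.9: "All AEs will be presented in a listing, which will specify whether they are treatment emergent or not".

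Notable laboratory abnormalities (sections 2.3.3 and 8.3.1) are counted over the treatment period. Section 3.6 defines that as 17 or 26 weeks according to the allocated regimen.

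Section 1 says that for DS-TB "the experimental arm (4BPaMZ) will be compared to the control arm (HRZE/HR) in all analyses", unless otherwise stated. Sections 2.3 and 8 say that safety is descriptive and untested.

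**The concern.** A crude proportion with at least one event rises with the time over which events are counted. Here that time differs between the randomised arms by design, and the plan has no common window, person-time rate or time-to-first-event summary for adverse events to set beside it.

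Take a hospital admission in week 22. For a control participant on schedule it enters the TEAE tables. For a 4BPaMZ participant on schedule it is a post-treatment event and reaches no adverse-event table.

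The stake is interpretation. Section 1 expects the trial to support that BPaMZ is safe and well tolerated. With no tests planned, a reader relies on the percentages printed side by side. A lower figure on 4BPaMZ could reflect less toxicity, a shorter count, or both. An early excess on 4BPaMZ could be offset by control events that accrue in weeks 19 to 28.

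**Working it through.** **Inputs.** Treatment lengths are 119 and 182 days (section 3.6). The TEAE window ends 14 days after the last dose (section 2.3). Adequate treatment on the 4-month regimen must be completed "within 175 days of starting therapy", and on the 6-month regimen within 238 days (section 3.3). The SAP gives no adverse-event rates and no timing, so those below are assumptions.

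**Reproducing the plan's lengths.** 17 × 7 = 119 and 26 × 7 = 182 days. Phases: 8 + 9 = 17 and 8 + 18 = 26 weeks. With the 56-day halt: 119 + 56 = 175 and 182 + 56 = 238 days. All agree with the SAP.

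**TEAE windows for participants who complete on schedule.**
- 4BPaMZ: (119 + 14)/7 = 133/7 = 19 weeks.
- HRZE/HR: (182 + 14)/7 = 196/7 = 28 weeks.
- Ratio: 28/19 = 1.47, or 19/28 = 0.68 the other way.
- With the full halt in both arms: (175 + 14)/7 = 27 and (238 + 14)/7 = 36 weeks, still nine weeks apart.

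For notable laboratory abnormalities the windows are 17 and 26 weeks, again nine weeks apart.

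**Effect on the proportions when the event hazard is the same in both arms.** Let p28 be the control proportion over 28 weeks. For a Weibull hazard with shape k, the 4BPaMZ proportion over 19 weeks is

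p19 = 1 − (1 − p28)^((19/28)^k).

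A constant hazard is k = 1, with exponent 0.679. For front-loaded events take k = 0.5, with exponent 0.824.

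| HRZE/HR, 28 weeks | 4BPaMZ, 19 weeks, constant hazard | Gap (points) | 4BPaMZ, 19 weeks, front-loaded (k = 0.5) | Gap (points) |
|---|---|---|---|---|
| 10% | 6.9% | 3.1 | 8.3% | 1.7 |
| 30% | 21.5% | 8.5 | 25.5% | 4.5 |
| 50% | 37.5% | 12.5 | 43.5% | 6.5 |

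Example: 1 − 0.70^0.679 = 0.215 and 1 − 0.70^0.824 = 0.255.

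Under a constant hazard, 4BPaMZ could have a weekly event rate 47% higher than control (28/19 = 1.47) and show the same percentage. If no first events occur between weeks 19 and 28, the gap is zero. With one common window, equal hazards give equal proportions and the gap is zero whatever the timing.

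**Which outputs are affected.**
- Affected: the TEAE tables of section 8.2 and Note to File 2, and the notable laboratory counts of sections 2.3.3 and 8.3.1.
- Not affected in this way: all-cause mortality, which covers the whole study (sections 2.3.1 and 8.1); the AST/ALT limb of the hepatotoxicity proportion (8.2.8.3), which has no TEAE limit, although its hepatic SAE limb refers back to the TEAE-based section 8.2.8; the laboratory shift tables (8.3.1); and the vital-sign, ECG, hormone and lens summaries, which extend past treatment (8.3.2 to 8.6).

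**The case against.** The strongest reply is that the TEAE definition is conventional and coherent. The regimens differ in length, and fewer on-treatment events is a real property of a shorter course. No safety hypothesis is tested, so nothing inferential fails. All of this stands. It is a reason to keep the TEAE tables and not to call the analysis invalid. It does not let a reader separate shorter counting from lower toxicity, because the TEAE proportion is the only adverse-event measure that is tabulated.

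A second reply is that the constant-hazard figures may overstate the gap. Control participants go from four drugs to two at week 8 (section 1.1), so events may cluster early. This also stands: the front-loaded column roughly halves the gap, and the SAP gives no basis for choosing between the two.

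A reader might infer more than the document supports: that the whole safety comparison favours 4BPaMZ by construction, or that a raised transaminase in week 22 on 4BPaMZ is left out of every table. Neither holds. Deaths are tabulated over the whole study, and a late AST or ALT rise can enter the hepatotoxicity table, which is not limited to the TEAE window. The gap in the plan concerns adverse-event proportions and notable laboratory counts.

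Finally, events per person-week are not a clean remedy. They assume a constant hazard. If events cluster early, the extra control weeks dilute the control rate and tilt the comparison against 4BPaMZ.

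**Conclusion.** The point holds for the adverse-event proportions in section 8.2 and Note to File 2 and for notable laboratory abnormalities. Followed as written, the plan gives percentages that are confounded with regimen length, and it leaves post-treatment adverse events without a table.

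With equal hazards and control proportions of 10% to 50%, the apparent advantage of 4BPaMZ is about 3 to 12.5 points under a constant hazard and about 2 to 6.5 points under the front-loaded assumption. It is nil if first events do not occur in weeks 19 to 28. These figures rest on assumed rates and timing, and on nominal windows for participants who complete on schedule. Early stopping shortens a participant's window and halts lengthen it.

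No planned test is affected. The harm is to interpretation, and a companion table should be added.

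**What to change.** Keep the TEAE tables. In section 8.2, for the two DS-TB arms, add companion tables of overall, grade 3–4, serious and liver-related adverse events that count TEAEs and post-treatment events together from Day 1 to week 28 in both arms. In section 8.3.1, add the notable laboratory abnormalities over the same window. Add a summary of post-treatment adverse events by arm.

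An exposure-adjusted rate may be given as a supplement, with a note that it assumes a constant hazard. It should not replace the common-window tables.

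The cost is a few extra tables. Section 1 provides 2 years of follow-up for all participants, and section 8.2.9 already lists and flags every adverse event. The common window includes off-treatment time on 4BPaMZ, so it relies on adverse events being collected similarly in both arms to week 28, and on comparable laboratory sampling for the laboratory table. The SAP alone does not settle this. It should be checked against the protocol and stated in a footnote.

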### **2.3.1. All-cause mortality**

The proportion of participants who died from any cause during the study.

### **2.3.2. Treatment emergent adverse events (TEAEs)**

#### **2.3.2.1. Incidence**

The proportion of participants who experienced at least one treatment-emergent adverse event (TEAE).

#### **2.3.2.2. Severity**

Of those experiencing at least one TEAE the highest grade experienced. The highest grade experienced is defined as the most extreme severity captured on the Adverse Event CRF page. The possible severities are 'Grade 1: Mild,' 'Grade 2: Moderate,' 'Grade 3: Severe', and 'Grade 4: Potentially life-threatening.'

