#### **2.3.2.4. Seriousness**

Proportion of participants experiencing at least one serious TEAE. A serious AE (SAE) is defined as any untoward medical occurrence that at any dose results in death, is life-threatening, is a congenital anomaly/birth defect, requires in-participant hospitalisation or prolongation, results in significant disability/incapacity, or is a medically important event.

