## 5. Analysis Populations

Analysis populations are:

- The **Intent to treat (ITT)** population, defined as all participants who were enrolled, whether or not they started treatment.
- The **Safety** population, defined as all enrolled participants who received at least one dose of study treatment. Participants will be analysed as to the treatment they actually received regardless of given allocation.
- The **Modified intent to treat (mITT)** population, defined as all participants who were enrolled and started treatment, excluding any late screening failures.
- The **TB-specific modified intent to treat (TB-mITT)** population, defined as the mITT population with additional exclusions (see below).
- The **Per-protocol (PP)** population, defined as the TB-mITT population with additional exclusions (see below).

For ITT, mITT, TB-mITT and PP; participants will be analysed as to the treatment they were randomised to receive.

For short-term culture conversion endpoints, only the mITT population will be examined.

The TB-mITT population is unique to the TB field and is outlined here (with further details provided in [Appendix §13.3](#)). TB-mITT is a key analysis that has been used in the literature of long-term outcome trials of durable cure in TB, although it has generally been referred to simply as the ‘mITT analysis’. This analysis excludes participants based on data collected post-randomisation. A true mITT analysis, as recognised by regulatory authorities, does not exclude any participants due to missing data post-enrollment.

Thus, for the long-term endpoint of durable cure, the TB-mITT analysis will be considered primary for the purposes of publication, to allow comparison with the rest of the literature in the TB field. However, for regulatory purposes, we recognise that regulatory agencies will consider the mITT analysis primary.

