### **8.2.2. Severity**

A summary of TEAEs by maximum severity will be presented in a table. In the TEAE severity table, if a participant reported multiple occurrences of the same TEAE, only the most severe TEAE is presented. TEAEs that are missing severity will be presented in tables as 'Severe' but will be presented in the data listing with a missing severity. A separate table will be presented for 'Grade 3: Severe' or 'Grade 4: Potentially life-threatening' TEAEs.

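### The TEAE severity outcome (SAP 2.3.2.2) covers only participants who had a TEAE, and 8.2.2 names no denominator, so the severity percentages may not compare the treated groups

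*SAP*

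**What the plan says.** Section 2.3 sets a default for the safety outcomes: "All safety summaries in this section will be presented for all participants in the Safety population, as defined in §5, unless otherwise stated". Section 5 gives the Safety population as "defined as all enrolled participants who received at least one dose of study treatment", so having an adverse event plays no part in membership.

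Within section 2.3.2, severity is the only outcome framed on a subset: "Of those experiencing at least one TEAE the highest grade experienced". The other outcomes there (incidence, relatedness, seriousness, discontinuation of treatment or study, death, liver-related events) are proportions of participants. Seriousness, for example, is "Proportion of participants experiencing at least one serious TEAE".

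On presentation, section 8.2.2 says "A summary of TEAEs by maximum severity will be presented in a table" and adds a separate table for grade 3 or 4 events. It names no denominator for either. Section 8.2.1 gives the number and percentage of participants with any TEAE. Sections 2.3 and 8 state that safety is descriptive, without tests.

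On how TEAEs arise, section 1.2 says: "Participants, trial Investigators and staff, including laboratory staff, will not be blinded to treatment allocation during the treatment phase of the trial". Section 3.6 sets the treatment period at 17 or 26 weeks by regimen, and section 2.3 counts TEAEs up to 14 days after the last dose.

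**The concern.** Having at least one TEAE is itself an outcome of treatment. A severity percentage taken among those participants divides by a number that can differ between arms for reasons unrelated to severe events:

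- **Reporting.** Staff and participants know the allocation, so mild events may be recorded more readily in one arm.
- **Time at risk.** For participants who complete treatment, the planned TEAE window is about 17 + 2 = 19 weeks on 4BPaMZ and 26 + 2 = 28 weeks on HRZE/HR.
- **Drug effect.** One regimen may cause more mild events.

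A participant with only mild events enters the denominator but not the grade 3–4 numerator. The arm with more such participants therefore shows a lower grade 3–4 percentage relative to the other arm, with no change in how many people had a severe event. Because no tests are planned, the displayed percentages are the comparison a reader will make.

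**Working it through.** The SAP states no severity or TEAE rates, so there is no planned figure to reproduce. All rates and counts below are assumptions. The arm size of 150 is the per-arm DS-TB figure in section 4; with equal arms, the size does not affect the ratios.

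**Notation, per arm.** N = Safety-population total; T = participants with any TEAE; G = participants whose highest grade is 3 or 4.

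- Risk among all treated = G/N.
- Share under the 2.3.2.2 wording = G/T.

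**Relation between the two.** With equal N, for arms A and B:

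(G_A/T_A) ÷ (G_B/T_B) = (G_A/G_B) ÷ (T_A/T_B)

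The ratio shown equals the severe-event risk ratio divided by the TEAE-incidence ratio. The two agree only if TEAE incidence is equal. If A has the higher severe-event risk, the order reverses exactly when

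1 < G_A/G_B < T_A/T_B.

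**Scenarios (assumed counts, 150 per arm, A v B).**

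| | T | T/N | G | G/N | G/T | Reversed? |
|---|---|---|---|---|---|---|
| a | 140 v 105 | 93.3% v 70.0% | 42 v 36 | 28.0% v 24.0% (+4.0 points) | 30.0% v 34.3% (−4.3) | yes |
| b | 135 v 120 | 90.0% v 80.0% | 40 v 37 | 26.7% v 24.7% (+2.0) | 29.6% v 30.8% (−1.2) | yes |
| c | 143 v 135 | 95.3% v 90.0% | 42 v 41 | 28.0% v 27.3% (+0.7) | 29.4% v 30.4% (−1.0) | yes |
| d | 143 v 135 | 95.3% v 90.0% | 45 v 36 | 30.0% v 24.0% (+6.0) | 31.5% v 26.7% (+4.8) | no |
| e | 120 v 120 | 80.0% v 80.0% | 42 v 36 | 28.0% v 24.0% (+4.0) | 35.0% v 30.0% (+5.0) | no |

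Check of row a: 42/36 = 1.167 and 140/105 = 1.333, so 1.167 lies between 1 and 1.333. The ratio shown is 1.167/1.333 = 0.875, which equals 30.0/34.3.

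**Range of severe-event risk ratios that reverse the order.**

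| TEAE incidence, A v B (assumed) | Reversal range |
|---|---|
| 95% v 90% | 1 to 0.95/0.90 = 1.056 |
| 90% v 80% | 1 to 0.90/0.80 = 1.125 |
| 90% v 70% | 1 to 0.90/0.70 = 1.286 |
| 95% v 60% | 1 to 0.95/0.60 = 1.583 |

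If the severe-event risk in B is 24%, the first range covers risks in A up to 24% × 1.056 = 25.3%, and the third up to 24% × 1.286 = 30.9%.

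**What the wording fixes.** The Safety-population default in 2.3 gives way wherever a subsection states otherwise, and 2.3.2.2 can fairly be read as doing so. Section 8.2.2 does not restore the default explicitly. The rule in section 8 that a participant is counted once within each preferred term and system organ class settles the numerator, not the denominator. The SAP does name a denominator elsewhere, for example the ITT set for medical history in section 10.3.

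**The case against.** The strongest reply is that 2.3.2.2 defines no percentage. It defines a participant-level variable, the highest grade, which exists only for someone who had an event. Its opening words may say who has a grade rather than what to divide by. Nor does 8.2.2 restrict its tables to participants with a TEAE, so the Safety-population default could still govern them. This reading is possible. It leaves the denominator open in both sections, however, and the same one-line edit is needed.

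Three further objections stand and limit the weight of the point:

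- Safety is descriptive, and no decision rule uses the severity distribution.
- The incidence table gives T in each arm. If the severity tables show counts, the Safety-population percentage is one division away.
- Serious TEAEs, TEAEs leading to discontinuation and fatal TEAEs are not defined conditionally on having a TEAE, so the safety package as a whole does not conceal severe harm.

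A reader might infer that the plan will make the more harmful regimen look milder. The SAP does not support that. It gives no event rates, and the direction is not fixed: the longer control period could raise TEAE incidence in the control arm just as drug effect or reporting could raise it in the experimental arm. When nearly everyone has a TEAE, reversal needs a very small true difference, as in row c.

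**Conclusion.** The point holds as a minor defect of definition. Read as written, the severity percentages rest on a denominator formed after treatment starts, and 8.2.2 does not correct this. The between-arm ratio is then off by a factor equal to the TEAE-incidence ratio: nil at equal incidence, 1.056 at 95% v 90%, and 1.286 at 90% v 70%. An actual reversal is confined to severe-event risk ratios between 1 and that factor.

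These sizes rest on assumed incidences and equal arms, and on reading 2.3.2.2 as setting the denominator. On the alternative reading the denominator is merely unspecified. In neither case does the SAP show that a reversal is likely, or which arm it would favour.

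**What to change.** - **Section 2.3.2.2:** define severity as the proportion of Safety-population participants in each arm by highest TEAE grade, with the categories none, 1, 2, 3 and 4.
- **Section 8.2.2:** state that percentages in both the maximum-severity table and the grade 3/4 table use the arm's Safety-population total as denominator, and show counts.

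A breakdown by grade among participants with a TEAE can be kept as an extra, provided it is labelled as such. The cost is SAP wording and a denominator setting in the table programs; the data are the same.
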